*Management of the project (co-ordinating investigator).* The Ph.D.-students involved in the project will benefit from being involved with researchers who have worked with clinical and epidemiological research in schizophrenia spectrum disorders for many years and from the excellent opportunities for international collaboration. All assessments will be carried out by researchers and Ph.D.-students, trained in all instruments used in the study before study start.

## Sharing of depersonalized data

We will share the depersonalized data at www.clinicaltrials.gov.

# Publications and dissemination policy

The OPUS YOUNG treatment approach will be manualized. Comprising a manual for CBCM, SCIT and MFG as it is delivered in OPUS YOUNG. Furthermore, and inspired by The Raise program for Coordinated Specialty Care for First Episode Psychosis in USA [87], we will offer the OPUS YOUNG manual online designed to guide implementation of future OPUS YOUNG team together with education programs that cover core elements in OPUS YOUNG treatment. Results from the analysis of data in OPUS YOUNG will be published in peer-reviewed international scientific journals.

#### PhD projects

The OY trial has planned five PhD studies (A-E):

A. The characteristics of the study population and pathways to care, the use of health care, and social services prior to study inclusion based on baseline data from all included participants and data from the Danish National Registers. (2021-2023)

B. Benefits and harms of OY vs. TAU: Analysis of the primary and secondary/exploratory outcomes of the RCT and testing the two main hypotheses, 1) that OY is more effective than TAU in improving social functioning, and 2) that OY will be more effective than TAU in reducing positive and negative psychosis symptoms and provide a higher client satisfaction and health related quality of life. Furthermore, the PhD will analyze self-efficacy, experience of service, treatment alliance and adherence, the use of pharmacotherapy, school adherence, family burden, siblings' perceived stress, substance misuse, and adverse treatment effects. This PhD will also analyze the sustained effects at 6 months follow-up for OY vs. TAU. (2023-2026)

C. User perspectives on trans-sectorial activities in OY vs. TAU: The primary focus in this PhD is to investigate and describe the trans-sectorial activities (the collaborations of OY/TAU with municipal and school services) and analyze whether the amount and quality of trans-sectorial activities is an effect moderator for outcomes at 24 months (end of trial) and 30 months (follow-up). Drawing on semi-structured interviews at approx. 24 months (end of trial, follow-up), clinical, and register data the study includes perspectives from patients, parents/legal caretakers, clinicians, and municipal collaborators on trans-sectorial activities and the quality of the collaboration.(2024-2026)

D. Clinical and cognitive Illness trajectories in OY vs TAU: To explore the detailed symptomatic and diagnostic illness trajectories as well as the cognitive and social cognitive trajectories during the first two years of early onset psychosis. Cluster analysis will be used to determine psychosis subgroups based on symptom/cognitive deficits heterogeneity and their course. Growth mixture

modeling (GMM) analysis will be used to identify distinct treatment response patterns for OY vs. TAU. The results will substantiate efforts to individualize future treatments based on patient subgroup profiles. Predictors of treatment effects will be evaluated using all available information from the examinations during the trial and the Danish National Registers. (2024-2026)

E. Cost-effectiveness of OY vs. TAU: To investigate the cost-effectiveness of OY vs. TAU, in to inform decision makers concerning the cost and benefits of the OY intervention. Cost-utility analyses (CUA) will be carried out for the trial period. The CUAs will be conducted from an extended health sector perspective and include the costs of all interventions directed toward the individual youth's mental health problems no matter the provider of services. Uncertainty about the long-term effects limits the possibilities of carrying out formal decision analytic modelling but can be handled by analyzing different possible scenarios in extrapolation scenarios of the development in health-related quality of life (HRQoL). Costs (of OY and TAU) will be estimated at the individual participant level. Youths are assessed for HRQoL using the Child Health Utility 9-Dimension (CHU-9D) and EQ-5D. CHU-9D is a generic preference-based HRQoL-measure constructed for use in youth and adults. We will measure the value of health outcomes in Quality-Adjusted Life Years (QALY). Health states will be defined using CHU-9D and EQ-5D. We will analyze the Incremental Cost-Effectiveness Ratio (ICER). (2024-2026)

The PhD studies will benefit from the international collaboration with highly experienced researchers with expertise in clinical and epidemiological research in schizophrenia spectrum disorders.

We will communicate all trial results, both positive, negative as well in-conclusive results, to health-care professionals, service users, policy makers and other relevant groups.

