# Study assessments of included participants, parents/legal caretakers, clinicians, and municipal collaborators.

All included patients and their parents/legal caretakers participate in a baseline assessment. Some of the baseline data will be assessed by interviews or questionnaires, while others, such as the standard clinical interview, will be obtained from the patients' medical journal.

Table 1 shows the assessment schedule for the research baseline and follow-up assessments for patients and parents/legal caretaker. In total, outcome assessments will be conducted four times during the study period; at baseline (entry into the study), after 12 months, after 24 months (treatment endpoint), and after 30 months (follow-up assessment 6 months after treatment endpoint). Parents/legal caretakers will be assessed and included in the overall data collection. The research appointments (baseline, 12, 24 and 30 months) will be registered in the participant's medical journal, but no research data will be registered in the medical journal. Clinician-rated working alliance will be assessed at 24 months. Clinicians and municipal collaborators will additionally be invited to participate in semi-structured interviews around the same timepoint. The interviews will focus on trans-sectorial collaboration and activities and will include demographic information such as professional background, age, sex and current employment and function.

Table 1 study assessment	schedule						
Patient assessment			Assessment time, months				
Topic:	Instrument/measure:	Adm*	A*	0	12	24	30
Demographics	Demographic information I			X	Χ	Χ	Х
Duration of untreated	Interview based on IRAOS	Ι		X			
psychosis							
Primary and comorbid	K-SADS-PL (full)	Ι	Х		Х	Х	
diagnoses	SCAN 2.1 (section 17, 18, 19)						
Positive and negative	SAPS, SANS	Ι		X	Х	Х	Х
symptoms							
Affective symptoms	YMRS	Ι		X	X	X	Х
	HAM-D (6 items)						
Global psychopathology	CGI-S,	IR		X	Х	Х	Х
	CGI-I	IR			X	X	X
Social function	PSP	Ι		Х	Х	Х	X
Intelligence	WISC-V (<16 years), WAIS-IV (≥16 years)	Т	Х				
Cognitive function	BACS	Т		X		X	
Social cognition	Hinting Task + EIMT	Т		X		X	
Quality of life	KIDSCREEN-10	Q		X	X	X	X
Quality-adjusted life year	CHU9D + EQ5D Q			X		X	X
Self-efficacy (general)	GSE Q			X	X	X	X
Working alliance	WAI Q				X	X	X
Client satisfaction	CSQ Q				X	X	
Negative effects of psych.	NEQ	Q				X	
treatment	atment						
Trauma	rauma Self-reported stressful life-events Q			X			

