#### Register-based information

Data on the patients will be extracted at 30 months (6 months follow-up after end-of-trial) from the following registers from Statistics Denmark: The Danish Population Register, the Danish Psychiatric Central Register, the Danish Education Register, the Danish Register of Special Education, the Danish Institution Register, the Danish Register of School Grades, the Danish Patient Register, the Danish Prescription Register, and the Danish Migration Register. We will assess socio-demographic information including school attendance, school grades and exams, labour market affiliation, civil status, cohabitation status, data on complications to the pregnancy and birth of the participant, education, living in an institution (and type of institution), use of any health care and social services and, in the unlikely event: cause of death.

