#### Randomization

After baseline assessment the participants will be randomized 1:1 to either the experimental treatment (OPUS YOUNG intervention) or standard treatment (TAU). Randomization of the

participant will be centralised and computerised with concealed randomization sequence carried out by the database system used in the Capital Region of Denmark (REDCap) [61]. The randomization concealment mechanism is performed by a computer algorithm saved in REDCap [61]. Randomization cannot be influenced by persons, and block size will be unknown for investigators and clinicians. To optimize the comparability between treatment groups, randomization will be stratified by the two factors: *age* (12-14 years and 15-17 years) and for the main outcome, *PSP* (score 1-44 and score 45-100).

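### Project D does not limit predictors of treatment effect to data from before randomisation, so variables that treatment can change are admitted as predictors

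*Protocol*

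**What the plan says.** Protocol, PhD projects, project D, sets out three linked analyses.

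- Subgroups: "Cluster analysis will be used to determine psychosis subgroups based on symptom/cognitive deficits heterogeneity and their course". The course in question covers the "cognitive and social cognitive trajectories during the first two years of early onset psychosis", which is essentially the randomised treatment period.
- Response classes: growth mixture modelling, where the "analysis will be used to identify distinct treatment response patterns for OY vs. TAU".
- Effect predictors: "Predictors of treatment effects will be evaluated using all available information from the examinations during the trial and the Danish National Registers".

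The purpose is also given: "The results will substantiate efforts to individualize future treatments based on patient subgroup profiles".

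Three other places fix the timing.

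- The section on study assessments says that "outcome assessments will be conducted four times during the study period; at baseline (entry into the study), after 12 months", then at 24 and 30 months.
- The Randomization section says: "After baseline assessment the participants will be randomized 1:1".
- The section Register-based information says: "Data on the patients will be extracted at 30 months".

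No section restricts the effect predictors, or the variables that define the subgroup profiles, to information from before randomisation.

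**The concern.** A predictor of treatment effect has to be a characteristic that the allocated treatment cannot have altered. Randomisation then makes the arms comparable at each level of it, and the predictor-by-arm interaction can be interpreted. A 12-month symptom score, or use of services during the two treatment years, does not qualify. Patients who reach a given level under OPUS YOUNG differ from those who reach the same level under TAU, and holding the variable fixed removes the part of the effect that runs through it.

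There is also a practical problem. The stated aim is to help individualise future treatment. A clinician choosing treatment for a new patient has baseline findings and history, but no 12- or 24-month result. A predictor built on later data cannot serve that aim even if it is estimated without bias.

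**Working it through.** **Timing.** Examinations take place at 0, 12, 24 and 30 months, and randomisation follows the examination at 0. Three of the four are therefore post-randomisation. The registers are extracted at 30 months and include use of health care and social services, so entries dated after inclusion can be available at extraction.

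**Inputs for the illustration.** Project D states no figure of its own. The SD of 13 and the difference of 5 PSP points come from Protocol, Sample size calculation. The total there reproduces: 42 × (13/5)² = 283.9, stated as 284.

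Two inputs are assumptions, because the protocol gives neither:

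- 12-month effect d12 of 2.5 or 5 points;
- correlation r between visits of 0.3 to 0.7.

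The true 24-month effect is set to 5 for everyone, so there is no real effect modification.

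**Formula.** Split all patients at the pooled median of the 12-month score, which lies d12/2 above the TAU mean. With normal scores, the 24-month arm difference in the upper half is

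effect = 5 + r × 13 × [λ(−a) − λ(a)], where a = (d12/2)/13 and λ(x) = φ(x)/(1 − Φ(x)).

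By symmetry the lower half gives the same value.

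- d12 = 2.5: a = 0.0962; λ(−a) = 0.3971/0.5383 = 0.7377; λ(a) = 0.3971/0.4617 = 0.8601; 13 × (0.7377 − 0.8601) = −1.59.
- d12 = 5: a = 0.1923; λ(−a) = 0.3916/0.5762 = 0.6796; λ(a) = 0.3916/0.4238 = 0.9242; 13 × (0.6796 − 0.9242) = −3.18.

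**Effect within each half of the 12-month score (truth: 5)**

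| r | d12 = 2.5 | d12 = 5 |
|---|---|---|
| 0.3 | 5 − 0.48 = 4.52 | 5 − 0.95 = 4.05 |
| 0.5 | 5 − 0.80 = 4.20 | 5 − 1.59 = 3.41 |
| 0.7 | 5 − 1.11 = 3.89 | 5 − 2.23 = 2.77 |

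The range is about 2.8 to 4.5, an understatement of roughly 10% to 44%. A simulation of 2,000,000 patients per scenario, with equal correlation between all visits, agrees to within 0.05 (for example 4.51/4.52 at r = 0.3, d12 = 2.5, and 2.79/2.79 at r = 0.7, d12 = 5).

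**Other splitting variables in the same simulation**

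| Split on | Effect within halves | Share in better half, OPUS YOUNG / TAU |
|---|---|---|
| Baseline score | 4.97 to 5.03 | 50% / 50% |
| 12-month score | 2.8 to 4.5 | 54–58% / 42–46% |
| 24-month score | about 1.8 | 58% / 42% |
| Change 0–24 months | about 3.4 | 56–60% / 40–44% |
| Change 0–12 months | about 5.0 | 53–60% / 40–47% |

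The lack of bias for the 0–12 month change follows from the assumed equal correlations between visits. Even there, membership of the better half depends on arm. Only the baseline split keeps both the effect and the balance between arms.

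**The case against.** Several points on the other side stand.

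- **Subgroups.** A reader might infer that OPUS YOUNG and TAU will be compared within the course-based clusters or the growth mixture classes. The protocol does not say so. Clustering is to determine subgroups, and the mixture model is to identify response patterns by arm. Describing trajectories by arm is legitimate. The point rests on the sentence about effect predictors.
- **Registers.** A reader might infer from extraction at 30 months that register data are consequences of treatment. The extraction date is not the date of the data: the same section lists pregnancy and birth complications, and project A uses the registers for service use before inclusion. Only entries dated after inclusion are at issue.
- **False predictors.** A reader might take the illustration to show that non-predictors would appear as predictors. It does not. The two halves give the same value, so no interaction is created. What it shows is attenuation, for a median split that the protocol does not itself propose.
- **Baseline data.** The predictor set includes the baseline examination, so part of it is sound, and the sentence could be read as merely naming two data sources.

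It can also be said that predictor lists and time windows for an exploratory project belong in an analysis plan, which is not at hand. This does not dispose of the point. The protocol is not silent: it names the set as everything available from the trial examinations and registers, and a plan that followed that wording would carry the fault forward. The wording about individualising treatment is modest, but even as hypothesis generation it needs predictors known before treatment is chosen.

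**Conclusion.** The point holds, as a minor one confined to project D. As worded, the predictor sentence admits variables that treatment can change. Arm contrasts across levels of such variables are not randomised comparisons and do not serve the stated purpose.

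The illustrated size, 2.8 to 4.5 points in place of 5, rests on the assumed correlations and 12-month effects and on a split of the 12-month PSP score. It shows the direction and plausible order of the distortion and does not forecast this trial's result. The primary PSP comparison and the sample size of 284 are not affected. The planned sensitivity analyses use age at inclusion, a baseline variable, and do not share the fault.

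**What to change.** In the protocol's description of project D, qualify the predictor sentence. Candidate predictors of treatment effect, and any subgroup profiles used for that purpose, should come only from the baseline examination and from register data dated before randomisation, and should be tested as predictor-by-arm interactions. Add that course-based clusters and growth mixture classes are descriptive outcomes and not strata within which OPUS YOUNG and TAU are compared.

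The cost is a short edit and fewer candidate predictors. No new data are needed, and the later examinations remain available as outcomes and for describing trajectories.
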